Recombinant human chorionic gonadotropin (r-hCG)(Ovidrel® Prefilled Syringe, Serono) will be purchased from Serono, Inc., Rockland, MA or Switzerland. Participants will receive a subcutaneous injection of 250 microgram-recombinant hCG three times a week (Monday, Wednesday and Friday) for 12 weeks. The first dose of study drug will be administered by a registered nurse. At that time, she will instruct each participant in the self-administration of the study drug in a skin fold of the upper abdominal region. Participants will return to receive doses 2 and 3, where they will be observed by the registered nurse in the self-administration of the drug for mastering of the skill and to answer any additional questions. The remainder of the drug doses will be self-administered by the participants or a partner trained in the procedure in their homes. All participants will be seen by a study physician once a month during the treatment phase for a history and physical exam and blood collection.

Protocol tissue collection

Normal breast tissue specimens will be collected by CNB at the beginning of treatment (0 day), at the end of treatment (90 days) and at six months post-treatment (270 days - 36 weeks). CNB specimens will be primarily utilized for analysis of genomic expression by cDNA microarray, RNA sequencing and epigenomic studies. In addition, a series of surrogate intermediate markers such as cytomorphologic evaluation and cell proliferation index will be analyzed. The primary objective is to compare the gene expression, and epigenomic profiles of sampled breast epithelial cells across the three time points (Fig. 1), before and after treatment, and identify differentially expressed or silenced genes (as determined by ≥ 2 fold change). Gene expression measurements will be obtained at baseline (time 0), after treatment with hCG at 90 days (time 1), and at 270 days from baseline (time 2). We are interested in comparing the expression profiles between all pairs of time points as well as across time. The comparison of profiles before and after treatment with either hCG, both at 90 and 270 days, are of particular interest (Figure 1).

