All the tubes containing CNB samples collected as described need to be kept at 4°C before shipping. As an additional measure each sample tube should be wrapped with Parafilm to prevent possible leakage during shipment. The samples have to be shipped by overnight express mail to the Breast Cancer Research Laboratory at the Fox Chase Cancer Center with frozen ice packs in the Styrofoam box. The samples need to be packed tightly so they do not move during shipping. The shipments should be sent Monday through Thursday to ensure the samples are collected accordingly and not to ship on *Fridays to ensure that the samples do not sit for an extended period of time.*

Special Studies

The following special correlative studies will be performed:

- #1, Histopathological evaluation of epithelial cell normality;
- #2, evaluation of cell proliferation by Ki67 immunohistochemistry;
- #3, serum analysis for hormone level and biomarker determinations;
- # 4, genomic analysis of breast epithelial cells from CNB.

Genomic DNA and total RNA will be extracted using ALLPrep DNA/RNA Mini Kit (QIAGEN) according to manufacture instructions.

Special Correlative study #1 - Cell Morphology and Proliferation:

Histopathological analysis - Outcome measures: A minimum of two slides will be made one for histology and another one for Ki-67.

Special Correlative study #2 - Cell proliferation - Ki67 index:

Total epithelial cells will be delineated with Mayer's hematoxylin counter stain and proliferating cells with a MIB-1 (DAKO M7240) antibody for Ki-67.

Special Correlative study #3 - Serum analysis for hormone level and biomarker determination:

At the time of each CNB, whole blood will be collected by venipuncture and stored in the FCCC Breast Cancer Research Laboratory at -80°C for batch determination of hormonal levels and aliquots will be stored for future studies. All serum assays for estradiol, progesterone and human chorionic gonadotropin will be conducted at the Breast Cancer Research Laboratory of the FCCC.

Special Correlative study #4 - Gene expression analysis.

Affymetrix U133plus2.0 microarrays will be used in this follow-up gene expression study involving 25 women each in the hCG treatment arm. Gene expression measurements will be obtained at baseline (before treatment) and at 3 months and 9 months after the respective treatment. We will identify genes that are

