significantly up or down regulated at 3 months following treatment. In addition, we will compare the post- and pre-treatment differences and identify genes showing significantly altered expression. We will repeat the above analyses using the post-treatment expression at 9 months.

Analysis of biomarker data.

In addition to microarray data, we will obtain expression levels of Ki67, ER, PR, estradiol, progesterone and hCG using serum assays at baseline (before treatment) and at 3 months and 9 months after treatment. We will identify markers that are significantly up or down regulated at 3 months following treatment. In addition, we will compare the post- and pre-treatment differences and identify markers showing significantly altered expression. We will repeat the above analyses using the post-treatment expression at 9 months.

Statistical Considerations.

The primary efficacy analyses for the phase I/II study will concern baseline to 3-month follow-up changes in gene expression profiles measured by microarray methods as follows. For each woman i at biopsy time point j (0 =pre-treatment, 1 =3 month follow-up) we will compute the Mahalanobis distance between RMA normalized expression microarray data derived from the biopsy and the prototypic gene profile. We will denote this distance as $D(i,j)$. If $D(i,1) < D(i,0)$ we will declare woman i a “success”. This would indicate the post-treatment profile (genomic signature) is closer than the pre-treatment profile to the prototypic gene profile. At the conclusion of the study we will sum the number of successes for each arm. Whichever arm has a higher proportion of successes is declared the “preventive choice”. With complete pre-treatment and post-treatment expression microarray data on 25 women we will correctly identify the changes in terms of “success” with at least 85% probability. Assuming a drop-out rate of 20%, we would need to enroll a total of 25 participants per arm.

In secondary analyses we will use an exact one-sided, one-sample test ($\alpha=0.05$) to assess the null hypothesis of no drug induced change in $D(i,j)$ (i.e., a null hypothesis that the probability of “success” is 0.5.). With data from 18 women we will have at least 80% power to detect the alternative hypothesis that the true probability of “success” is 0.80. We will also characterize the change in distance (i.e., $\Delta D(i)=D(i,1)-D(i,0)$) using standard methods (e.g., mean, median, standard deviations, etc.).

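### The exact test's null of 0.5 means no systematic change from any cause, so with one treated group its 5% level does not cover attribution to hCG

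*Protocol*

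**What the plan says.** Statistical Considerations calls woman i a success if her Mahalanobis distance to the prototypic gene profile is smaller at 3 months than at baseline. A secondary exact one-sided, one-sample test at 5% is then used "to assess the null hypothesis of no drug induced change in" D(i,j), which the text restates as "a null hypothesis that the probability of “success” is 0.5". The power statement reads "With data from 18 women we will have at least 80% power" to detect "the alternative hypothesis that the true probability of “success” is 0.80".

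The opening summary describes 25 women, all treated for 12 weeks, and the Dutch summary calls the study open. Statistical Considerations speaks of arms and of a control group, but the protocol defines no second arm.

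Under Inclusion criteria, women who were taking oral contraceptives or hormone replacement may enter if they stopped six weeks before treatment and the baseline biopsy. Protocol tissue collection sets the next biopsy at day 90.

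**The concern.** The protocol treats two hypotheses as one. A success probability of 0.5 means that a woman's 3-month distance is as likely to be above as below her baseline distance. This is the same as no effect of the drug only if, without hCG, the two specimens would be exchangeable as regards D. Nothing in the design secures or estimates that, because no group shows the success probability without hCG. The 9-month sample comes from the same treated women and is no control.

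This is the only hypothesis test that the protocol sets out for the distance endpoint. The Specific aim is proof of principle that treatment reverts the signature, and the exploratory analyses are also described in terms of changes induced by the drug. A rejection is therefore likely to be read as causal, with a 5% error rate that does not apply to that reading.

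**Working it through.** **Inputs from the protocol.** One-sided exact binomial test, level 0.05, p0 = 0.5, p1 = 0.80, n = 18. With 25 enrolled and 20% drop-out, 25 × 0.8 = 20 women remain; with no drop-out, 25.

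**The plan's own figure.** For n = 18 and p = 0.5, P(X ≥ 13) = (8568 + 3060 + 816 + 153 + 18 + 1)/2^18 = 12616/262144 = 0.048. P(X ≥ 12) = 31180/262144 = 0.119 is too large, so the rule is to reject at 13 or more. At p = 0.80 the power is 0.867. The claim of at least 80% is correct. The corresponding rules are 15 of 20 (level 0.021, power 0.804) and 18 of 25 (level 0.022, power 0.891).

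**Rejection with no drug effect.** Let ΔD = D(i,1) − D(i,0) be normal with standard deviation σ. Suppose a non-drug cause shared by all follow-up samples lowers its mean by δ. Then P(success) = P(ΔD < 0) = Φ(δ/σ), and the rejection probability is the binomial tail at that value. The protocol gives no δ/σ, so these are assumed values.

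| δ/σ toward the prototype | P(success) | n = 18 (≥13) | n = 20 (≥15) | n = 25 (≥18) |
|---|---|---|---|---|
| 0 | 0.50 | 0.048 | 0.021 | 0.022 |
| 0.10 | 0.54 | 0.093 | 0.046 | 0.052 |
| 0.25 | 0.60 | 0.21 | 0.12 | 0.15 |
| 0.50 | 0.69 | 0.50 | 0.38 | 0.47 |

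**The opposite direction.** Suppose hCG alone would give P(success) = 0.80 (δ/σ = 0.84) and a shared non-drug change reduces this to 0.70 (δ/σ = 0.524), an unfavourable shift of 0.84 − 0.524 ≈ 0.32 SD. Power falls from 0.867 to 0.534 at 18 women, from 0.804 to 0.416 at 20, and from 0.891 to 0.512 at 25.

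**Direction in a multivariate distance.** A simulation with no drug effect used 18 women, 20 dimensions, identity covariance, a baseline gap of 3, and between- and within-woman SDs of 0.7 (all assumed). A shared shift of 0.5 units in the expression space gave:

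- toward the prototype: P(success) 0.62, rejection 0.26;
- orthogonal: P(success) 0.49, rejection 0.04;
- away: P(success) 0.37, rejection 0.003.

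**A time-linked difference in the text.** A woman who stopped hormones exactly six weeks before baseline has been off them for 42 days at the first biopsy and 42 + 90 = 132 days at the second. This affects only women who were taking them, and the protocol does not say how many there are or in which direction D would move.

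**The case against.** The strongest reply is that every single-arm before/after study has this limit and that this one is open about its nature. It calls itself proof-of-concept and exploratory, the test is secondary, the bracketed restatement fixes the tested hypothesis as 0.5, and the primary decision rule does not use the test. All of that is true, and the test and its power are correctly specified. It limits the weight of the point but does not make the two hypotheses equivalent.

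A reader might go further in four ways that the documents do not support:

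- *Any shared shift inflates the error rate.* Only a shift toward the prototype does. A shift in an arbitrary direction tends to increase a multivariate distance. In simulations with randomly directed shared shifts at 20 women (for example 20 or 100 dimensions, identity covariance), P(success) was at most 0.50 and rejection lay between 0 and 3.5%.
- *More women make it worse.* Not over the range this trial can reach. In the table 18 women is the worst case, because the attained level jumps with n.
- *The arrays are left open to batch shifts.* Serum is "stored in the FCCC Breast Cancer Research Laboratory at -80°C for batch determination of hormonal levels", and for the arrays only RMA normalisation is named. But the protocol does not say that arrays are run visit by visit, and hybridisation order may be set in a document not shown here. The silence is not a fault.
- *Regression to the mean explains a success.* Women are not selected on D, so it is not an obvious cause.

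**Conclusion.** The point stands as one of interpretation. The arithmetic of the test is right, but its null is described as something the design cannot test. The 5% level applies to no systematic change in D between baseline and 3 months (a median ΔD of zero), whatever the cause.

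The figures rest on an assumed shared shift toward the prototype and a normal ΔD. For shifts of 0.25 to 0.5 SD, rejection without a drug effect ranges from 0.12 to 0.50 over 18 to 25 women. The documents show neither that such a shift exists nor which way it would go. The hormone wash-out is one difference between the visits that the text itself supports, and its effect on D is unknown. It would be wrong to conclude that the test is anti-conservative in general, or that a single-arm design is unacceptable for this purpose. What does follow is that a rejection cannot by itself be credited to hCG.

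**What to change.** Restate the null as no systematic change in D from baseline to 3 months, P(success) = 0.5. Remove *drug induced* from the null and from the conclusion drawn from it. Report a rejection as a change over the treatment period, not as an effect shown to be caused by hCG. Reconcile the references to arms and to a control group with the one-group design. The cost is wording and a less favourable claim; sample size and procedures are unchanged.

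As an optional safeguard, run each woman's baseline and follow-up arrays in the same batch with one joint RMA, or confirm that this is already planned. It removes technical shifts only. Time-linked biological differences, such as time off hormones, would remain, so it does not replace the rewording. Its cost is later array results.

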In exploratory analyses we will use LIMMA to identify genes whose expression changes significantly from pre- to post-treatment. Statistical significance will be measured by p-values adjusted for FDR using the method of Benjamini and Hochberg (108). Genes showing an FDR of less than 5% will be considered statistically significant. Biological significance will be measured by fold change. Genes showing more than 2-fold change in either direction (up and down regulated) will be considered biologically significant. Differentially expressed genes from each of the above filters will be combined and a list of common genes showing greater statistical and biological significance (lower q-values and up/down regulated by more than 2-fold) will be identified. Finally, we will use various bioinformatics methods (pathway analyses, enrichment analyses, etc.) to extract additional biological insights into the drug-induced changes in normal breast tissue. All of the above analyses will be repeated to examine baseline to 9-month follow-up differences. Assuming approximately 20000 genes of relevance in the study, a total sample size of 36 women/arrays (i.e., 18 each) will enable us to detect effect sizes of 1.39, 1.32 and 1.27 if the number of truly differentially expressed genes is 500, 1000 and 1500 respectively, with a power of 80% and a false discovery rate (FDR) of 5%. These calculations are based on the approach outlined in (105). In terms of \log_2 expression, an effect size of 1.32 corresponds to a 2.5-fold difference in gene expression between the control group and each treatment.

Mining for pathways and exploratory analyses:

In this study we are proposing two major high throughout genomic data platforms such as microarray and next generation sequencing platforms. The data mining and bioinformatics pipelines for both platforms are different. Following is a description of these data analyses pipelines.

Microarray data Mining:

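### The gene-level power statement matches two independent groups of 18 and a control group, not this one-group paired trial, and its 2.5-fold translation needs an unstated SD of 1 log2 unit

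*Protocol*

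**What the plan says.** All of this is in the protocol, Statistical Considerations, in the paragraph on exploratory analyses.

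- The analysis is within women: "we will use LIMMA to identify genes whose expression changes significantly from pre- to post-treatment".
- The power statement reads: "a total sample size of 36 women/arrays (i.e., 18 each) will enable us to detect effect sizes of 1.39, 1.32 and 1.27". Its assumptions are some 20000 relevant genes, 80% power and an FDR of 5%. The three effect sizes belong, in that order, to 500, 1000 and 1500 genes that truly change.
- The effect size is then translated on the log2 scale: "an effect size of 1.32 corresponds to a 2.5-fold difference in gene expression between the control group and each treatment".
- The gene list also passes through a fold-change filter: "Genes showing more than 2-fold change in either direction (up and down regulated) will be considered biologically significant".

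Elsewhere, the opening summary has 25 women, all treated with Ovidrel. The section on protocol tissue collection has each woman biopsied at baseline, 90 days and 270 days. No section gives an SD of log2 expression, an SD of the within-woman change, or a within-woman correlation.

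**The concern.** The power sentence and the analysis it supports describe different designs. LIMMA is to be applied to change within a woman, but the effect is described as a contrast between a control group and more than one treatment. This trial has neither. In a paired design, the detectable effect is naturally expressed in SDs of the within-woman difference. Converting that to SDs of a single array requires the within-woman correlation.

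The fold-change sentence has a separate fault. A standardised effect is a difference divided by an SD, so it becomes a log2 difference only after multiplication by that SD. Without the SD, a reader cannot tell what fold change the trial can detect. That matters because the same paragraph filters genes at 2-fold.

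**Working it through.** **Inputs (protocol, Statistical Considerations).** m = 20000 genes; m1 = 500, 1000 or 1500 truly changed; power 80%; FDR 5%; 18 and 18 arrays. Two-sided testing is implied by changes in either direction. The power method is cited to an outside source that is not at hand, so the formula below is an assumption.

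**Step 1: per-gene significance level.** alpha = 0.05 × 0.8 × m1 / [(m − m1) × 0.95].

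- m1 = 500: 20 / 18525 = 0.00108
- m1 = 1000: 40 / 18050 = 0.00222
- m1 = 1500: 60 / 17575 = 0.00341

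**Step 2: reproduce the plan's figures.** Two independent groups of 18, SD 1, two-sided normal approximation: d = (z[1 − alpha/2] + 0.842) × √(2/18), where √(2/18) = 1/3.

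| m1 | z[1 − alpha/2] | d, two groups | Stated | Power at stated d |
|---|---|---|---|---|
| 500 | 3.269 | 1.37 | 1.39 | 81.6% |
| 1000 | 3.060 | 1.30 | 1.32 | 81.6% |
| 1500 | 2.928 | 1.26 | 1.27 | 81.1% |

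The stated effects each need 18 per group by this formula. A one-sided two-sample t calculation is about as close (1.40/1.31/1.25). The two-sided t version gives 1.49/1.40/1.34.

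**Step 3: the design the trial has.** With 18 pairs and the effect in SDs of the within-woman difference:

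- Normal approximation, (z[1 − alpha/2] + 0.842)/√18: 0.97/0.92/0.89.
- Noncentral t, 17 degrees of freedom: 1.15/1.07/1.02.

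No paired variant tried in these units, one- or two-sided, normal or t, gives 1.39/1.32/1.27.

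**Step 4: which way the mismatch runs.** If the stated effects d are in SDs of a single array and rho is the within-woman correlation, the paired effect is d / √(2(1 − rho)). Power with 18 pairs (two-sided t; rho is an assumed range):

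| rho | m1 = 500 | 1000 | 1500 |
|---|---|---|---|
| 0 | 60% | 64% | 66% |
| 0.2 | 75% | 77% | 78% |
| 0.3 | 82% | 84% | 85% |
| 0.5 | 95% | 96% | 96% |

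The break-even correlation is 1 − (d/dz)²/2, with dz from the t calculation in Step 3. For m1 = 500 it is 1 − (1.39/1.151)²/2 = 0.27; for the other two it is 0.24 and 0.22. On the normal approximation, rho = 0 returns the two-group power of Step 2, so the shortfall at low correlation comes from using the t distribution with 17 degrees of freedom.

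**Step 5: the fold change.** log2(2.5) = 1.322 and 2^1.32 = 2.50, so the standardised effect was used directly as a log2 difference. In general the fold change is 2^(1.32 × SD). For assumed SDs of 0.3, 0.5, 0.7, 1.0 and 1.3 log2 units, this is 1.32-, 1.58-, 1.90-, 2.50- and 3.29-fold.

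**The case against.** The best defence is that the sample-size phrase mixes women and arrays and can be read as 18 pre-treatment plus 18 post-treatment arrays, which fits the planned comparison. On that reading, the two-group formula simply ignores the correlation. With moderate positive correlation this is conservative, as Step 4 shows. That point stands and limits the consequence. It does not rescue the reference to a control group and several treatments, and it supplies no SD.

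A second defence also stands: the paragraph is labelled exploratory, and the enrolment of 25 is justified by the distance-based success analysis earlier in the section. It is true that the tissue-collection section names the comparison of expression profiles, with a 2-fold criterion, as the primary objective. Even so, no sample size or decision rule rests on this power statement.

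Three stronger readings are tempting, and the protocol does not support them.

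- **That the plan has well under 80% power at its own 2-fold threshold.** On an SD of 1, 2-fold is an effect of 1.0. Two groups of 18 would then have 39/48/53% power (normal) or 31/40/45% (t). Those figures belong to the two-group design that this trial does not have, and to an SD the protocol does not state. For 18 pairs with per-array SD 1, power (t) is 41/52/58% at correlation 0.3, 62/72/78% at 0.5 and 91/95/97% at 0.7. The protocol also claims 80% power only at its stated effect sizes, not at 2-fold. The 2-fold rule is a filter on observed change, which a gene with a true change of exactly 2-fold passes about half the time at any sample size.
- **That the figures can only have come from a two-group calculation.** The match is close but approximate, and the source method is not available.
- **That the analyst will ignore the pairing.** The text speaks throughout of pre- to post-treatment change, and the exact LIMMA model may properly be left to the SAP.

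**Conclusion.** The point holds as a correction of a stated figure. The effect sizes 1.39/1.32/1.27 closely match two independent groups of 18, and the accompanying sentence names a control group. The trial has one treated group with paired arrays, so the statement does not describe it. The size and direction of the error depend on a correlation the protocol does not give: conservative from about 0.3 upwards, optimistic near zero (60-66% rather than 80%, t-based, 18 pairs). The 2.5-fold translation is unsupported in either direction without an SD, and power at a true 2-fold change cannot be determined without both the SD and the correlation.

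These conclusions rest on the assumed FDR-based per-gene alpha and two-sided testing. The contradiction over the control group and the missing SD depend on no calculation.

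**What to change.** - Restate gene-level power for paired differences, naming the number of evaluable pairs. For 18 pairs, 80% power and 5% FDR, the detectable mean change is about 1.15/1.07/1.02 SDs of the within-woman log2 change for 500/1000/1500 true genes (two-sided t). The trial statistician should confirm these against the cited method before they enter the protocol.
- Quote a fold change only with a stated SD of the paired log2 difference and its source, as 2^(effect × SD).
- Delete the comparison with a control group and each treatment, and the description of the sample as 18 in each of two sets.

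The cost is a recalculation and a few lines of text. Enrolment, biopsies and the planned analyses do not change.
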